12.5.3 Pharmacokinetics

Descriptive summary statistics will be provided by dose and visit/sampling time point,
Comercially Confidential Information

Summary statistics will include mean (arithmetic and geometric), SD, CV (arithmetic and geometric), median, minimum, and maximum.

Comercially Confidential Information

Table 12-1 Non-compartmental pharmacokinetic parameters

AUClast	The AUC from time zero to the last measurable concentration sampling time (tlast) (mass x time x volume-1)
AUCtau	The AUC calculated to the end of a dosing interval (tau) at steady-state (amount x time x volume-1)
Cmax	The maximum (peak) observed plasma, blood, serum, or other body fluid drug concentration after single dose administration (mass x volume-1)
Tmax	The time to reach maximum (peak) plasma, blood, serum, or other body fluid drug concentration after single dose administration (time)
T1/2	The elimination half-life associated with the terminal slope (λ_z) of a semi logarithmic concentration-time curve (time). Use qualifier for other half-lives

Comercially Confidential Information

12.6 Analysis of exploratory endpoints

Commercially Confidential Information

12.6.1 Biomarkers

For the biomarker analyses only the LNP023 CCI 200mg –treated and rituximab-treated subjects will be included.

Commercially Confidential Information

The effect on the treatment over time will be assessed

Commercially Confidential Information

A scatterplot of UPCR from first morning void and 24h urine UPCR at each visit will be performed to assess UPCR from first morning void as a monitoring marker.

Commercially Confidential Information

The disease severity at baseline and the relationship with anti-PLA2R will be assessed graphically.

Commercially Confidential Information

12.7 Interim analyses

Commercially Confidential Information

12.8 Sample size calculation

12.8.1 Primary endpoint(s)

A total of approximately 52 subjects will be recruited into the study: approximately 24 on LNP023 200 mg, approximately 24 on rituximab

Commercially Confidential Information

This number is based on several assumptions: the assumed treatment effect, the variability of the primary endpoint log UPCR as well as on the assumed drop-out rate of 17% (i.e. 9 subjects).

With data from 40 subjects for the analysis of the primary efficacy variable, there is 80% chance that the predefined efficacy criteria (Section 12.4.2) will be met, assuming the true reduction of UPCR of LNP023 200 mg vs. rituximab is 8% (i.e. (ratio from BL in UPCR_LNP)/ (ratio from BL in UPCR_Ritux) = 0.92). If the true increase of LNP023 200 mg vs. rituximab is 55% (i.e. (ratio from BL in UPCR_LNP)/ (ratio from BL in UPCR_Ritux) = 1.55) the chance of meeting the efficacy criteria is around 14%.

Commercially Confidential Information

13 Ethical considerations and administrative procedures

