This is a randomized, open-label, two arm, parallel group, proof-of-concept, non-confirmatory study evaluating the efficacy and safety of LNP023 compared with rituximab in subjects with MN at high risk of disease progression defined on the basis of anti-PLA2R antibody titer (≥ 60 RU/mL) and proteinuria (≥ 3.5 g/24h) (please refer to protocol [Section 5.1](#) for details).

A total of approximately 52 subjects will be randomized into the study: approximately 24 on LNP023 200 mg, approximately 24 on rituximab

Commercially Confidential Information
Treatment with LNP023 or rituximab is open label.
Commercially Confidential Information

Efficacy will be evaluated at the end of the 24-week period. The randomization ratio is 1:1 (LNP023: rituximab).

Commercially Confidential Information

Commercially Confidential Information

24h urine samples will be collected by the subject at home on the morning of the day prior to the indicated study visit and brought to the study site on the day of visit: samples will be collected 1) at run-in, 2) for baseline, 3) between Day 112 and Day 113, and 4) between Day 168 and Day 169 (end of treatment).

First morning void samples for monitoring of UPCR and other safety urine parameters will be collected 11 times by the subject at home: 1 time at run-in, 1 time for baseline, 7 times during the treatment period and 2 times during safety follow-up.

Pharmacokinetics, safety and other assessments will be conducted according to the study schedule (see [Section 8](#)). Safety assessments will include physical examinations, ECGs, vital signs, standard clinical laboratory evaluations (hematology, blood chemistry and urinalysis), adverse event and serious adverse event monitoring.

Commercially Confidential Information

Total study duration from screening until end of study (EOS) is approximately 65 weeks.

The study includes (see [Figure 3-1](#)):

- a screening visit
- a run-in period of up to 12 weeks
- a baseline visit
- Day 1 (day of first investigational drug administration)
- a treatment period of 24 weeks
- a follow-up period without any treatment of 29 weeks, including the EOS visit

Commercially Confidential Information

Screening period

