4.4 Purpose and timing of interim analyses/design adaptations

Commercially Confidential Information

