11.3 Site monitoring

Before study initiation, at a site initiation visit or at an investigator's meeting, a Novartis or delegated CRO representative will review the protocol and data capture requirements (i.e. eCRFs) with the investigators and their staff. During the study, Novartis employs several methods of ensuring protocol and GCP compliance and the quality/integrity of the sites' data. The field monitor will visit the site to check the completeness of subject records, the accuracy of data capture / data entry, the adherence to the protocol and to Good Clinical Practice, the progress of enrollment, and to ensure that study treatment is being stored, dispensed, and accounted for according to specifications. Key study personnel must be available to assist the field monitor during these visits. Continuous remote monitoring of each site's data may be performed by a centralized Novartis/delegated CRO/CRA organization. Additionally, a central analytics organization may analyze data & identify risks & trends for site operational parameters, and provide reports to Novartis clinical teams to assist with trial oversight.

The investigator must maintain source documents for each subject in the study, consisting of case and visit notes (hospital or clinic medical records) containing demographic and medical information, laboratory data, electrocardiograms, and the results of any other tests or assessments. All information on CRFs must be traceable to these source documents in the subject's file. The investigator must also keep the original informed consent form signed by the subject (a signed copy is given to the subject).

The investigator must give the monitor access to all relevant source documents to confirm their consistency with the data capture and/or data entry. Novartis monitoring standards require full verification for the presence of informed consent, adherence to the inclusion/exclusion criteria, documentation of SAEs, and of data that will be used for all primary variables. Additional checks of the consistency of the source data with the CRFs are performed according to the study-specific monitoring plan. No information in source documents about the identity of the subjects will be disclosed.

12 Data analysis and statistical methods

The analysis will be conducted on all subject data at the time when an interim analysis occurs or when the trial ends.

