12.4.2 Statistical model, hypothesis, and method of analysis

To assess the primary objective, UPCR will be analyzed using a mixed model for repeated measures. The results will be back transformed and presented on the original scale.

Commercially Confidential Information

The following two criteria will be used to assess treatment efficacy:

- Statistically significant decrease (no worse than 55% increase) in UPCR at week 24 visit in LNP023 200 mg -treated subjects vs. rituximab-treated subjects at one-sided 10% level (i.e. $H_0 : (\text{ratio from BL in UPCR_LNP}) / (\text{ratio from BL in UPCR_Ritux}) \geq 1.55$)
- Estimated mean reduction in UPCR in LNP023 200 mg-treated subjects better than 10% increase vs rituximab-treated subjects (i.e. $(\text{ratio from BL in UPCR_LNP}) / (\text{ratio from BL in UPCR_Ritux}) < 1.1$)

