#### **6.1.3 Statistical model, assumptions and hypotheses**

To assess the primary objective, the log-transformed ratio to baseline in UPCR will be analyzed using a mixed model for repeated measures (MMRM). The results will be back transformed and presented on the original scale.

Commercially Confidential Information

Commercially Confidential Information

The following two criteria will be used to assess treatment efficacy (both criteria must be satisfied for success):

- Statistically significant decrease (no worse than 55% increase) in UPCR at week 24 visit in LNP023 200 mg-treated subjects vs. rituximab-treated subjects tested at one-sided 10% level from a lower-tailed test (i.e.  $H_0 : (24 \text{ week to baseline ratio in UPCR in LNP023 200 mg}) / (24 \text{ week to baseline ratio in UPCR Rituximab}) \geq 1.55$ )
- Estimated mean reduction in UPCR in LNP023 200 mg-treated subjects better than 10% increase vs rituximab-treated subjects at week 24 visit (i.e.  $(24 \text{ week to baseline ratio in UPCR in LNP023 200 mg}) / (24 \text{ week to baseline ratio in UPCR in Rituximab}) < 1.1$ )

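### The stated 14% chance of success at a true ratio of 1.55 cannot arise from the 10% test described for the 40-subject analysis, and it needs reconciling with the 80% and the 10%

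*Protocol*

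**What the plan says.** **The decision rule.** Protocol 12.4.2 and the synopsis set two efficacy criteria on the week-24 ratio to baseline in UPCR, LNP023 200 mg relative to rituximab. Criterion 1 rejects the hypothesis that this ratio of ratios is 1.55 or more, for "rituximab-treated subjects at one-sided 10% level". Criterion 2 asks for an estimated ratio of ratios below 1.1. SAP 6.1.3 repeats both, with criterion 1 "tested at one-sided 10% level from a lower-tailed test", and adds that "both criteria must be satisfied for success".

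**The operating characteristics.** Protocol 12.8.1 refers back to the 12.4.2 criteria. With 40 analysed subjects, "there is 80% chance that the predefined efficacy criteria" are met if the true ratio is 0.92. If the true ratio is 1.55, "the chance of meeting the efficacy criteria is around 14" percent.

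**Interim analyses.** The opening of Protocol Section 12 says that analysis is done "at the time when an interim analysis occurs or when the trial ends". Protocol 4.4 is headed "Purpose and timing of interim analyses/design adaptations". The content of Protocol 4.4 and 12.7 and of SAP Section 3 is blacked out, as is text directly after the 14% sentence and text just before the criteria in Protocol 12.4.2 and SAP 6.1.3.

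**Status of the study.** Protocol Section 3 calls it a "proof-of-concept, non-confirmatory study".

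**The concern.** The value 1.55 appears twice in different roles. In 12.4.2 it is the edge of the null hypothesis, where a one-sided 10% test should succeed 10% of the time. In 12.8.1 it is the true value at which success is put at about 14%. A second compulsory criterion can only lower the chance of success, so the 12.8.1 figure is above the ceiling set by the rule to which it refers.

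The figure has a practical meaning: it is the risk of a positive proof-of-concept decision when proteinuria on LNP023 is truly 55% worse than on the active comparator. A reader of 12.4.2 or SAP 6.1.3 would put that risk at no more than 10%. A reader of 12.8.1 would put it at 14%. The 80% comes from the same calculation, so doubt about one figure extends to the other.

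**Working it through.** **Inputs from the documents.** Margin 1.55, ln = 0.4383. Criterion 2 threshold 1.1, ln = 0.0953. Planning effect 0.92, ln = −0.0834. One-sided level 10%, z = 1.2816. Forty analysed subjects, randomized 1:1.

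**Assumptions.** 20 subjects per arm. The SD of the log ratio is not readable, so it is solved from the stated 80% and also varied.

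**Formula for one analysis.** SE = SD × √(2/20). Success requires the estimated log ratio to lie below both ln 1.55 − 1.2816 × SE and ln 1.1. For a true log ratio θ:

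P(success) = Φ((min(0.4383 − 1.2816 × SE, 0.0953) − θ) / SE).

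**Step 1: the ceiling.** At θ = 0.4383, criterion 1 alone gives Φ(−1.2816) = 10.0%, whatever the SE. With criterion 2 also required, the chance is at most 10.0%. A t test with an estimated SD gives the same maximum over SDs from 0.3 to 3.0. Using z critical values with an estimated SD raises it only to 10.4%.

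**Step 2: the stated 80%.** Suppose criterion 2 is the stricter one. Then (0.0953 + 0.0834) / SE = 0.8416, so SE = 0.1787 / 0.8416 = 0.2123 and SD = 0.2123 / √0.1 = 0.67. Check: the criterion 1 threshold is 0.4383 − 1.2816 × 0.2123 = 0.1662, which is above 0.0953, so criterion 2 does bind.

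**Step 3: the matching figure at 1.55.** Φ((0.0953 − 0.4383) / 0.2123) = Φ(−1.615) = 5.3%. The t-test version also gives 5.3%. Splits of 22/21 or 24/24 leave it at 5.3%, because fixing the 80% fixes the SE. If the stated 80% were rounded from 78% or 82%, the t-test result would be 6.7% or 3.9%.

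**Step 4: no SD gives both figures** (normal model, 20 per arm).

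| SD | Both criteria at 0.92 | Both criteria at 1.55 | Criterion 2 alone at 1.55 |
|---|---|---|---|
| 0.60 | 82.7% | 3.5% | 3.5% |
| 0.67 | 80.0% | 5.3% | 5.3% |
| 0.80 | 76.0% | 8.8% | 8.8% |
| 0.90 | 70.9% | 10.0% | 11.4% |
| 1.00 | 64.4% | 10.0% | 13.9% |

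Criterion 2 alone comes close to 14% only at an SD of 1.0. There its own chance of being met at 0.92 is Φ(0.1787 / 0.3162) = 71%, and the chance of meeting both is 64%. Neither is 80%.

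**Step 5: could an interim rule explain it?** Rules and timing are assumed here because the text is blacked out. In each case the final look keeps both criteria, and the SD is re-solved so that overall success at 0.92 is 80% (normal model).

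| Assumed interim success rule | Share of information at interim | Overall success at 1.55 |
|---|---|---|
| Same two criteria, 10% unadjusted | 40% / 50% / 60% / 70% | 15.0% / 14.5% / 13.9% / 13.2% |
| Interim estimate below 0.92 | 40% | 14.5% |
| Interim estimate below 1.0 | 50% / 60% | 16.4% / 12.5% |
| Interim estimate below 1.1 | 80% | 14.5% |

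A look that can stop only for futility lowers the figure (0.1% to 5.3% over the versions tried), and a scheme that holds the overall level at 10% keeps it at or below 10%. Neither of these explains 14%.

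**The case against.** The strongest reply is that the plan never says there is only one analysis. Interim analyses are foreseen, their rules are blacked out, and the blacked-out blocks sit where an explanation would normally stand. The last table shows that ordinary interim success rules give 80% and about 14% together. The sponsor also states the larger risk openly in 12.8.1, the study is non-confirmatory, and the decision rule does not use the 14%.

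Much of this stands. A reader might infer that the 14% is an arithmetic slip. The documents do not show that, because a hidden interim rule could produce it. A reader might instead infer that the 10% must be a per-look level and that the final analysis has only about 76% power. That is not supported either: rules based on the interim estimate alone also give about 14% while 10% applies only to the final test, and any final-look power depends on an assumed rule and a back-solved SD. Nor can an explanation be called missing from the plan when the relevant text is withheld.

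The reply does not remove the conflict in the text that can be read. Section 12.8.1 ties its figures to 40 analysed subjects and to the 12.4.2 criteria. The synopsis goes from the model description to the criteria without any per-look wording. Read as written, this is one analysis, and for one analysis 14% is impossible.

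**Conclusion.** The point holds in a limited form. For the 40-subject analysis as described, a 14% chance of success at 1.55 is incompatible with a one-sided 10% test of that same boundary. The ceiling is 10% (10.4% with z critical values and an estimated SD), and this part does not depend on the SD. If the 80% at 0.92 is right, the matching figure is about 5%; that part rests on 20 per arm and a back-solved SD of about 0.67.

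The public text cannot settle whether the 14%, the 80%, or only the description is at fault. The importance is moderate to low: these are stated operating characteristics of a non-confirmatory study, and the success rule itself is unaffected. It is still worth correcting, because two readable sections give different risks for the same wrong decision.

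**What to change.** Recompute both 12.8.1 figures from the planning SD, with the two criteria applied jointly. Then take whichever case applies:

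- **The figures describe the 40-subject analysis.** Replace the 14% with the recomputed value, which will be at most 10%. If the SD behind the 14% is the intended one, restate the 80% as well.
- **The figures include an interim success rule.** Say so in 12.8.1 and give the final-analysis figures beside the overall ones. Next to the 10% test level in the synopsis, Protocol 12.4.2 and SAP 6.1.3, state that the overall chance of success at 1.55 is about 14%. Call the 10% per-look only if the actual rule makes it so.

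The cost is one recalculation and one or two sentences in each place. Test level, margin, sample size and conduct stay as they are.

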13.1 Regulatory and ethical compliance

This clinical study was designed and shall be implemented, executed and reported in accordance with the International Conference on Harmonisation (ICH) Harmonized Tripartite Guidelines for Good Clinical Practice, with applicable local regulations (including European Directive 2001/20/EC, US CFR 21), and with the ethical principles laid down in the Declaration of Helsinki.

13.2 Responsibilities of the investigator and IRB/IEC

Before initiating a trial, the investigator/institution must obtain approval/favorable opinion from the Institutional Review Board/Independent Ethics Committee (IRB/IEC) for the trial protocol, written informed consent form, consent form updates, subject recruitment procedures (e.g. advertisements) and any other written information to be provided to subjects. Prior to study start, the investigator is required to sign a protocol signature page confirming his/her agreement to conduct the study in accordance with these documents and all of the instructions and procedures found in this protocol and to give access to all relevant data and records to sponsor monitors, auditors, sponsor Quality Assurance representatives, designated agents of sponsor, IRBs/IECs, and regulatory authorities as required. If an inspection of the clinical site is requested by a regulatory authority, the investigator must inform sponsor immediately that this request has been made.

13.3 Publication of study protocol and results

The protocol will be registered in a publicly accessible database such as clinicaltrials.gov and as required in EudraCT. In addition, after study completion (defined as last patient last visit) and finalization of the study report the results of this trial will be submitted for publication and posted in a publicly accessible database of clinical trial results, such as the Novartis clinical trial results website and all required Health Authority websites (e.g. Clinicaltrials.gov, EudraCT etc.).

For details on the sponsor publication policy including authorship criteria, please refer to the sponsor publication policy training materials that were provided to you at the trial investigator meetings.

13.4 Quality Control and Quality Assurance

Sponsor maintains a robust Quality Management System (QMS) that includes all activities involved in quality assurance and quality control, to ensure compliance with written Standard Operating Procedures as well as applicable global/local GCP regulations and ICH Guidelines.

Audits of investigator sites, vendors, and sponsor systems are performed by auditors, independent from those involved in conducting, monitoring or performing quality control of the clinical trial. The clinical audit process uses a knowledge/risk based approach.

Audits are conducted to assess GCP compliance with global and local regulatory requirements, protocols and internal SOPs, and are performed according to written sponsor processes.

14 Protocol adherence

This protocol defines the study objectives, the study procedures and the data to be collected on study participants. Additional assessments required to ensure safety of subjects should be administered as deemed necessary on a case by case basis. Under no circumstances including incidental collection is an investigator allowed to collect additional data or conduct any additional procedures for any purpose involving any investigational drugs under the protocol, other than the purpose of the study. If despite this interdiction prohibition, data, information, observation would be incidentally collected, the investigator shall immediately disclose it to Novartis and not use it for any purpose other than the study, except for the appropriate monitoring on study participants.

Investigators ascertain they will apply due diligence to avoid protocol deviations. If an investigator feels a protocol deviation would improve the conduct of the study this must be considered a protocol amendment, and unless such an amendment is agreed upon by Novartis and approved by the IRB/IEC and Health Authorities, where required, it cannot be implemented.



16 Appendices

Table 16-1 Definitions of Triggers, Actions and Follow-up requirements for liver events

Criteria	Actions required	Follow-up monitoring
Potential Hy's Law case (Elevated ALT/AST > 3 × ULN and TBL > 2 × ULN but without notable increase in ALP to > 2 × ULN – or 3 × ULN in the presence of bone pathology)	
 Discontinue the study treatment immediately Hospitalize, if clinically appropriate Establish causality (investigate alternative etiologies)^a Record the AE and contributing factors (e.g. concomitant medication, medical history, laboratory value) in the appropriate eCRF 	
 ALT, AST, TBL, Alb, PT/INR, ALP, GGT, CK and GLDH (frequency at Investigator discretion) Monitor for symptoms^b Report outcome^c
ALT or AST		
> 8 × ULN	
 Interrupt the study treatment Hospitalize if clinically appropriate Establish causality (investigate alternative etiologies)^a Study drug can be restarted only if alternative etiology is identified and liver enzymes return to baseline Record the AE and contributing factors (e.g. con meds, med hx, lab) in the appropriate eCRF 	
 ALT, AST, TBL, Alb, PT/INR, ALP and GGT (frequency at Investigator discretion) Monitor for symptoms^b Report outcome^c
> 3 × ULN and INR > 1.5 If elevated at baseline: > 2 x baseline or > 300 U/L (whichever occurs first)	
 Interrupt the study treatment Hospitalize if clinically appropriate Establish causality (investigate alternative etiologies)^a Study drug can be restarted only if alternative etiology is identified and liver enzymes return to baseline Record the AE and contributing factors (e.g. con meds, med hx, lab) in the appropriate eCRF 	
 ALT, AST, TBL, Alb, PT/INR, ALP and GGT until resolution (frequency at Investigator discretion)
> 5 to ≤ 8 × ULN If elevated at baseline: > 3 x baseline or > 300 U/L (whichever occurs first)	
 Repeat LFT within 48 hours If elevation persists, continue follow-up monitoring If elevation persists for more than 2 weeks, discontinue the study drug Establish causality (investigate alternative etiologies)^a Record the AE and contributing factors (e.g. con meds, med hx, lab) in the appropriate eCRF 	
 ALT, AST, TBL, Alb, PT/INR, ALP and GGT until resolution (frequency at Investigator discretion)

Criteria	Actions required	Follow-up monitoring

> 3 × ULN to ≤ 5 × ULN (accompanied by symptoms)^b
 
If elevated at baseline: > 2 x baseline or > 300 U/L (whichever occurs first)
	
 Interrupt the study treatment Hospitalize if clinically appropriate Establish causality (investigate alternative etiologies)^a Study drug can be restarted only if alternative etiology is identified and liver enzymes return to baseline Record the AE and contributing factors (e.g. con meds, med hx, lab) in the appropriate eCRF 	
 ALT, AST, TBL, Alb, PT/INR, ALP and GGT until resolution (frequency at Investigator discretion) Monitor for symptoms^b Report outcome^c

> 3 to ≤ 5 × ULN (patient is asymptomatic)^b
 
If elevated at baseline: > 2 x baseline or > 300 U/L (whichever occurs first)
	
 Repeat LFT within the next week If elevation is confirmed, initiate close observation of the subject 	
 Investigator discretion Monitor LFT within 1 to 4 weeks
ALP (isolated)		

> 2 × ULN (in the absence of known bone pathology)
 
>3 x ULN if bone pathology is present
	
 Repeat LFT within 48 hours If elevation persists, establish causality (investigate alternative etiologies)^a Record the AE and contributing factors (e.g. con meds, med hx, lab) in the appropriate eCRF 	
 Investigator discretion Monitor LFT within 1 to 4 weeks or at next visit
TBL (isolated)		

> 2 × ULN (in the absence of known Gilbert syndrome)
	
 Repeat LFT within 48 hours If elevation persists, discontinue the study drug immediately Hospitalize if clinically appropriate Establish causality (investigate alternative etiologies)^a Record the AE and contributing factors (e.g. con meds, med hx, lab) in the appropriate eCRF 	
 ALT, AST, TBL, Alb, PT/INR, ALP and GGT until resolution^c (frequency at Investigator discretion) Test for hemolysis (e.g. reticulocytes, haptoglobin, unconjugated [indirect] bilirubin)

> 1.5 to ≤ 2 × ULN (patient is asymptomatic)^b
	
 Repeat LFT within the next week If elevation is confirmed, initiate close observation of the subject 	
 Investigator discretion Monitor LFT within 1 to 4 weeks or at next visit

Criteria	Actions required	Follow-up monitoring
Jaundice	
 Interrupt the study treatment Hospitalize the subject Establish causality (investigate alternative etiologies)^a Study drug can be restarted only if alternative etiology is identified and liver enzymes return to baseline Record the AE and contributing factors (e.g. con meds, med hx, lab) in the appropriate eCRF 	
 ALT, AST, TBL, Alb, PT/INR, ALP and GGT until resolution (frequency at Investigator discretion) Monitor symptoms^b Report outcome^c
Any AE potentially indicative of a liver toxicity ^d	
 Consider study treatment interruption or discontinuation Hospitalization if clinically appropriate Establish causality (investigate alternative etiologies)^a Record the AE and contributing factors (e.g. con meds, med hx, lab) in the appropriate eCRF 	
 Investigator discretion

^a Serology tests, imaging and pathology assessments, hepatologist's consultancy; obtaining more detailed history of symptoms and prior or concurrent diseases, history of concomitant drug use, exclusion of underlying liver disease

^b Severe fatigue, malaise (general), abdominal pain (right upper quadrant), nausea, vomiting or rash with eosinophilia

^c Resolved = return to Day 1 values; Condition unchanged = stable values at three subsequent monitoring visits at least 2 weeks apart; Condition deteriorated = values worsen or liver transplantation; and Fatal.

^d These events cover the following: hepatic failure, fibrosis and cirrhosis, and other liver damage-related conditions; the non-infectious hepatitis; the benign, malignant and unspecified liver neoplasms.

TBL: total bilirubin; ULN: upper limit of normal

Liver event guidance for CRF completion is available in the Site Operations Manual.
